6.4.3 Planned Analyses

6.4.3.1 Primary Analyses

Primary Objective: Describe and analyze how individual differences and conditions influence adherence to preventive and acute migraine management strategies.

Phase 2 diary data will be utilized. Random effects logistic models will be used to examine the effects of individual differences (e.g., age and gender) and circumstances (headache days/last 7 days, variations in stress) on daily adherence to migraine management strategies during the initial three-month study period. The random effects logistic model is a kind of generalized linear mixed effects model which can take account of missing data due to drop outs. This type of analysis yields robust estimates even in situations when observations are missing both at random, and not at random. The total number of non-adherence days at the end of follow-up will also be obtained, and the effect of individual characteristics and conditions on the rate of non-adherence will be examined using Poisson regression model with log of length of follow-up as offset.

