6.4 Statistical Method

6.4.1 Statistical Design

Basic descriptive statistics (e.g., means, standard deviations, frequencies) for variables of interest will be computed. Graphical approaches will be used to further explore the data where appropriate. The outcomes are either 1) repeated measures of binary adherence to each migraine management strategy [coded each day as 0 (did not adhere) or 1 (adhered)] or total number of non-adherence days for each migraine management strategy over the relevant time-frame. Longitudinal binary outcomes will be analyzed using randomized logistic models, and number of total non-adherence days will be examined using Poisson regression models. SAS 9.3 will be used in the analyses. All tests are two-sided using significance level 0.05.

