6.4.2 Sample Size Considerations

Based on n=30 subjects in CDST and Headache Education Control groups, and assumptions of dropout rate and correlations as described in the initial phase of the study, we will have 80% power to detect an odds ratio of 1.28 in adherence to migraine management strategies between CDST and Headache Education Control.

For Phase 1b, we would like to estimate satisfaction, usability, and attrition over the course of the month of diary use. In our previous daily diary research, approximately 60% of participants do not continue using headache diary applications after 3 days, and approximately 30% of people adhere to the daily diary for the duration of a 30-day study. Therefore, we hope to obtain information from n=60 people regarding satisfaction and usability at the end of the 30-day period.

For the main phase of the study, based on estimated proportions of 0.37 for stress management, 20% with mood disorder and 30% male, cumulative drop-out rate of 0.073, 0.172 and 0.216 at the end of 1, 2, and 3 month, respectively, from previous studies 1, and assuming correlations of no more than 0.6 among repeated daily migraine management strategies, with n=100 participants, we can detect odds ratios of 1.29 between those with and without mood disorder, 1.26 between female and male, and 1.17 corresponding to 1 SD difference in continuous predictors, with 80% power.

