6.4.3.2 Secondary Objectives Analyses

Secondary Objective: Develop a tailored CDST to improve preventive and acute migraine management strategies.

Phase 3 diary data will be utilized. As described above, random effects logistic models will be used to examine the effects of Group (CDST vs. Headache Education Control), Time, and Group X Time on daily adherence to migraine management strategies. Poisson regression model with log of length of follow-up as offset will be used to examine differences between the groups on total number of nonadherence days at the end of the study.

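### The plain Poisson model for total non-adherence days does not control its error rate, and its follow-up-time offset makes the Treat Early count rise with headache frequency

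*Combined protocol and SAP*

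**What the plan says.** Section 6.4.1 defines two forms of the adherence outcome. One is daily, "coded each day as 0 (did not adhere) or 1 (adhered". The other is the "total number of non-adherence days for each migraine management strategy over the relevant time-frame", for which it says "number of total non-adherence days will be examined using Poisson regression models".

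Section 6.4.3.1, under Primary Analyses, gives the Phase 2 count model: "individual characteristics and conditions on the rate of non-adherence will be examined using Poisson regression model with log of length of follow-up as offset". Section 6.4.3.2 repeats it for the randomised comparison: "Poisson regression model with log of length of follow-up as offset will be used to examine differences between the groups".

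Random effects are named for the daily logistic model only. Sections 6.4.1, 6.4.3.1, 6.4.3.2, 6.4.4 and 6.4.5 give the count model no scale parameter, negative binomial form, robust variance or person-level term. On within-person correlation, section 6.4.2 says only "assuming correlations of no more than 0.6 among repeated daily migraine management strategies".

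Section 5.2.1 defines Treat Early by the pain level when acute medication is taken, which is recorded when the participant reports headache activity. Section 5.3.2 limits Phase 2 to people with 6 to 14 headache days a month.

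**The concern.** Poisson regression fixes the variance of the count at its mean. A total of correlated yes/no days has no reason to obey that, and two separate mechanisms pull in opposite directions. Stable differences between people raise the variance above Poisson, so the reported standard errors are too small. The bound on each day (0 or 1) lowers it below Poisson, so they are too large. The plan allows for neither.

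The offset is a second, independent problem. For Treat Early, the opportunity to be non-adherent is a treated headache, not a calendar day. Two people who treat early equally often will have different totals over the same follow-up if one has more headaches.

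The count model is listed under Primary Analyses and is also applied to the CDST comparison, and no rule says which model prevails if the logistic and count results disagree. An interval or p-value from it could therefore be reported as evidence on a predictor or on the CDST.

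**Working it through.** **Inputs.** Two-sided 0.05 (6.4.1). Adherence 0.37 for stress management, so non-adherence q = 0.63; correlation at most 0.6, structure not given; cumulative drop-out 0.073, 0.172 and 0.216 at months 1, 2 and 3; n = 100 in Phase 2 with 30% male (6.4.2). 30 per group in Phase 3 (6.1.2). Follow-up of three months, taken as m = 90 days. The correlation is an assumption, shown over a range.

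**The plan's own figures.** No power is stated for the count model. The stated figures, "we can detect odds ratios of 1.29 between those with and without mood disorder, 1.26 between female and male, and 1.17" per SD and "we will have 80% power to detect an odds ratio of 1.28 in adherence to migraine management strategies", concern odds ratios. The detectable log odds ratio is 2.80 / sqrt(p(1-p)k / (1/n1 + 1/n2)), with p = 0.37 and k effective days per person; the last bracket is 1/100 for the per-SD case. For 30 versus 30 without drop-out, independent days give 1.17, serial (AR(1)) correlation 0.6 gives 1.37, and equal correlation 0.6 between all days gives 3.21, against the stated 1.28. Solving for k, the odds ratios 1.28, 1.29, 1.26 and 1.17 imply 36.8, 32.5, 30.0 and 13.7 effective days. No single structure tried reproduces all four, so the correlation cannot be read off the plan.

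**Variance relative to Poisson, stable between-person correlation rho.** Ratio = (1-q)(1 + 89 rho) = 0.37(1 + 89 rho). True error of a nominal 5% test = 2(1 - Phi(1.96/sqrt(ratio))). The ratio is 1 at rho = (1/0.37 - 1)/89 = 0.019. The simulated columns (4,000 runs) use the stated drop-out.

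| rho | ratio | error, formula | simulated 70 v 30 | simulated 30 v 30 |
|---|---|---|---|---|
| 0 | 0.37 | 0.1% | - | - |
| 0.05 | 2.02 | 16.8% | 15.7% | 15.2% |
| 0.1 | 3.66 | 30.6% | 29.5% | 30.6% |
| 0.3 | 10.2 | 54.0% | 52.0% | 52.0% |
| 0.6 | 20.1 | 66.2% | 65.3% | 66.8% |

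If the 30 v 30 simulation keeps only people below 50% adherence, as Phase 3 entry does, the error at the same four non-zero correlations is 9, 16, 20 and 18%.

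**Purely serial correlation (AR(1)).** Ratio = 0.37(1 + 2 sum(1 - k/90) rho^k). At 0.1, 0.3, 0.46 and 0.6 the ratio is 0.45, 0.68, 0.99 and 1.45, and the error 0.4, 1.8, 4.9 and 10.3%. Simulation at 70 v 30 gives 0.3, 1.5, 5.2 and 10.2%.

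**Both together.** Stable correlation of 0.02, 0.05 or 0.1 plus serial 0.3 to 0.5 gives simulated errors of 7-13, 19-24 and 31-34%.

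**What a small stable correlation means.** rho = SD² / (0.37 × 0.63), where SD is the between-person spread in true adherence. An SD of about 7 percentage points is break-even (0.07²/0.233 = 0.021), 10 points gives 0.043 and 15 points gives 0.097.

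**Effect of a repair.** In simulation over stable correlations 0 to 0.6 (20,000 runs), a Pearson-scaled standard error with a t reference gives 5.0-6.0% and a robust one 3.9-5.6%. Under AR(1), the robust version reached 6.8% at 30 v 30.

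**Treat Early.** Suppose every headache day is treated and adherence is a for everyone. Non-adherent days per 90 are 3h(1-a) for h headache days a month. At a = 0.5 this is 9 for h = 6 and 21 for h = 14. The ratio is 14/6 = 2.33 at any a below 1; it should be 1. With the follow-up offset, all 400 simulated fits (n = 100, a = 0.5) found a significant headache-frequency effect. With log headache days as the offset the ratio returned to 1.00.

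**The case against.** The strongest reply is that 0.6 is a ceiling with no stated structure. Taken at face value over a mean of 79.4 days after drop-out, the four odds ratios imply design effects of 79.4/k = 2.16, 2.45, 2.65 and 5.81. Multiplied by 0.37, these are Poisson variance ratios of 0.80, 0.91, 0.98 and 2.15, or errors of 3, 4, 5 and 18%; three of the four show no inflation. This stands as a limit on how large a figure may be claimed, although one correlation structure should not yield four different design effects, so these are no secure estimate either. The 0.37 also applies to stress management alone.

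A reader might infer errors above 50% from the 0.6. That needs a stable correlation of 0.3 or more, which the documents do not state. A reader might also infer that neglecting between-person variation can err either way. It only makes standard errors too small; the opposite error comes from the bounded daily outcome.

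For Treat Early, a reader might infer that headache-free days could be coded 0, reversing the bias. That fits the documents poorly: recording is tied to headache activity, and the best attainable adherence would be 14/30 = 47%, so everyone within 6 to 14 headache days would meet the below-50% Phase 3 criterion. The 2.33 is itself the extreme contrast that eligibility allows.

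Reach is limited too. The count accompanies a logistic model that carries a person effect, and Phase 3 is a pilot. This lowers the severity but does not make the count model's intervals correct.

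**Conclusion.** The point holds and should be fixed. As written, the count analyses in 6.4.3.1 and 6.4.3.2 have no controlled error rate, and its size cannot be fixed from the documents. It is about 0.3-10% if correlation is purely serial (0.1 to 0.6), and about 16% and 30% at stable correlations of 0.05 and 0.1. These rest on 0.37 adherence and 90 days; Phase 3 selection reduces the inflation but does not remove it. Inflation is the more plausible direction, because the primary hypothesis and objective (4.1, 4.2) presuppose that adherence differs between people, and a spread of about 7 points is already break-even.

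The Treat Early offset is wrong whatever the correlation, with a rate ratio of up to 2.33 at equal adherence if all headaches are treated. It matters in Phase 2 for predictors related to headache frequency (6.4.3.1 names recent headache days as a predictor only for the logistic model), and in Phase 3 if headache days differ between arms.

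A reader might infer that the main adherence results are invalid. They are not shown to be: the random effects logistic model, named first, is free of the variance problem.

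**What to change.** In both 6.4.3.1 and 6.4.3.2, model non-adherent days out of assessable days per person with a beta-binomial or quasi-binomial model. Alternatively, keep Poisson with a Pearson-scaled, negative binomial or robust variance; the robust version needs a small-sample correction at 30 per group.

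For Treat Early, state that headache-free days are unscored and use the log of the number of scorable (acute-treated) headache days as the offset. In Phase 3 also report headache days and treated headache days by arm. Whether a headache is treated is a post-randomisation behaviour that the CDST Medication module (6.1) addresses, so the arms may be compared on differently selected days.

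The cost is a few sentences of SAP text and a few lines of SAS, with no new data. Intervals will usually be wider, and the Treat Early comparison becomes conditional on treated days, leaving untreated headaches out.

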5.3.2 ELIGIBILITY CRITERIA

Eligibility will be determined by a phone screen provided by a research assistant, supervised by the PI.

Inclusion/Exclusion Criteria Phase 1 (A & B):

Participants will be included if they 1) have an International Classification of Headache Disorders – 3 beta diagnosis of migraine, 2) self-report between 6 to 14 headache days per month, 3) are currently prescribed a triptan for acute migraine management, 4) are between the ages of 18 and 65, and 5) self-report at least one problem with adherence to preventive and acute migraine management strategies.

Exclusion criteria are 1) probable or confirmed medication overuse headache, 2) a plan to change, or changing preventive or acute migraine medication during study participation, and 3) are pregnant or are planning to become pregnant during study involvement (as triptans are Category C medications).

Inclusion/Exclusion Criteria Phase 2:

Participants will be included if they 1) have an International Classification of Headache Disorders – 3 beta diagnosis of migraine, 2) self-report and diary-confirmed 6 to 14 headache days per month, 3) are currently using one of the following treatments for acute migraine management: triptans, ditans, gepants, NSAIDs, or acetaminophen, 4) are stable on current preventive and acute treatment regimen for migraine, 5) are between the ages of 18 and 65, 6) reads English, 7) has capacity to consent, and 8) complete 80% of diary recordings in the first 30 days of monitoring.

Exclusion criteria are 1) probable or confirmed medication overuse headache, 2) a plan to change, or changing preventive or acute migraine medication during study participation, 3) are pregnant or are planning to become pregnant during study involvement (as triptans are Category C medications), 4) psychiatric illness or cognitive difficulties that would interfere with participation in the study, and 4) participated in Phase 1 of the Clinical Decision Support for Patient Migraine Management protocol.

Inclusion/Exclusion Criteria Phase 3:

Participants will be included if they 1) completed Phase 2 of the study, 2) completed at least 80% of diary recordings throughout Phase 2 of the study, and 3) demonstrated poor (<50%) adherence to at least one acute migraine management strategy and at least one preventive behavioral migraine management strategy during study Phase 2.

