6.3.5 On Study Visits

All study visits occur either over the phone or via scheduled REDCap data capture sessions, which are either accessed through the participant's email on any device, or through the study app on either the participant's personal Apple device or the study-provided Apple device.

Phase 1A & B

Screening

- Research coordinator will assess inclusion/exclusion criteria
- Approximately 20 minutes in length

App Testing

- Interact with CDST or Headache Education version of app 3 times daily for 7 days (Phase 1A) or 30 days (Phase 1B).
- Each diary entry will take between 1-5 minutes

Focus Group:

- At least one participant per focus group; Focus group led by the PI
- Up to 60 minutes in length
- Questions will focus on: 1) User Interface; 2) Message Content; 3) Message Delivery and Frequency, and 4) Overall Satisfaction

Phase 2 and 3

Screening

- Research assistant will assess inclusion/exclusion criteria with the supervision of the PI
- Approximately 30 minutes in length

Electronic Data Collection:

- App-based
- Phase 2: Month 0-Month 3
- Phase 3: Month 3-Month 6
- See schedule of assessments below

Table 6.1.3. Timing of Measures

Month 0 ~20 min.	Demographics Migraine Symptoms Medications Health literacy (Newest Vital Sign) E-health literacy (eHEALS) Pittsburgh Sleep Quality Index (first 4-items) Berlin Questionnaire
Month 0 Month 3 Month 7 ~40 min.	Migraine Disability Assessment Headache Management Self-Efficacy Acute Medication Self-Efficacy - Headache Study-Specific Self-Efficacy

	Outcome Expectancies Headache Specific Locus of Control Pain Catastrophizing Scale Five Factor Mindfulness Questionnaire Chronic Pain Acceptance Questionnaire
Monthly ~20 min.	Migraine Specific Quality of Life 2.1 PROMIS Interference Perceived Stress Scale PROMIS Anxiety PROMIS Depression PROMIS Sleep Disturbance Daily Stress Inventory
Daily	Morning (~3-5 min.) -Menstruation -Headache Symptoms -Acute Medication Usage -Sleep Behavior Afternoon (~1-2 min.) -Headache symptoms -Acute Medication usage Evening (~3-5 min.) -Preventive Medication Usage -Headache Symptoms -Acute Medication Usage -Eating and Hydration behavior -Stress Level and Management -Migraine Disability
Month 7 ~7 min.	Client Satisfaction Questionnaire Program Evaluation

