6.4.5 Handling of Missing Data

The random effects logistic model is a kind of generalized linear mixed effects model which can take account of missing data due to drop outs. This type of analysis yields robust estimates even in situations when observations are missing both at random, and not at random.

7. Trial Administration

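### The Poisson offset is length of follow-up, not days with the diary item answered, so on its ordinary reading an unanswered day acts as an adherent day

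*Combined protocol and SAP*

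**What the plan says.** Section 6.4.3.1 (Primary Analyses) adds a count analysis to the random effects logistic model: "The total number of non-adherence days at the end of follow-up will also be obtained", and its rate is to be "examined using Poisson regression model with log of length of follow-up as offset". Section 6.4.3.2 repeats this for the randomised comparison: "Poisson regression model with log of length of follow-up as offset will be used to examine differences between the groups".

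The count comes from the electronic diary (sections 5.2.1 and 6.2.1). Section 6.4.1 has adherence "coded each day as 0 (did not adhere) or 1 (adhered") and gives no code for an unanswered day. Section 6.4.5, the only section on missing data, describes the logistic model, "which can take account of missing data due to drop outs". It does not mention the Poisson counts, and length of follow-up is not defined anywhere.

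The plan expects skipped entries from people who remain in follow-up:
- Phase 2 eligibility asks for 80% of recordings in the first 30 days. Phase 3 entry requires that the person "completed at least 80% of diary recordings throughout Phase 2 of the study" (section 5.3.2). No completion floor is stated for the Phase 3 diary.
- Staff make contact after two consecutive days without data, and the participant continues (section 6.3.1).
- Diary completion is itself a listed outcome (section 5.2.2).

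Each item sits in one entry. Table 6.1.3 (section 6.3.5) places preventive medication in the evening ("Evening (~3-5 min.) -Preventive Medication Usage"), together with eating and stress. Sleep is in the morning entry.

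**The concern.** A day on which the item is unanswered adds to follow-up time but cannot add to recorded non-adherence, so the model treats it as adherent. The log follow-up offset shortens the denominator for someone who drops out, but not for someone who stays and skips evenings.

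Two things are at stake. Non-adherence rates are understated in everyone who skips the relevant entry. And if completion is related to a predictor (Phase 2) or to arm (Phase 3), part of the estimated rate ratio reflects completion, not behaviour. The group that answers less looks more adherent. The Poisson and logistic results could then disagree for this reason alone.

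**Working it through.** **Inputs from the documents.** Adherence 0.37, so non-adherence q = 0.63; 30 per arm; correlation between daily measures of at most 0.6 (all section 6.4.2). Phase 3 lasts three months, taken as 90 days (section 6.3.1). Two-sided 0.05 (section 6.4.1).

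**Assumed.** Item completion c, varied from 70% to 100%, because the documents give no figure by group.

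**The plan's own figure.** None is stated for the Poisson models. The nearest is 80% power for an odds ratio of 1.28 in Phase 3. I could not reproduce it: at correlation 0.6, two-sided power is about 9% if the correlation is exchangeable and 56% to 61% if it is first-order autoregressive, with no allowance for drop-out. The plan does not state the correlation structure, so I do not call the figure wrong. It serves below only as a yardstick.

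**Step 1: recorded days.** Expected count = 90 × c × q. The rate per day of follow-up is c × q, and the adherence it implies is 1 − c × q.

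| Completion | Recorded non-adherence days | Implied adherence (true value 37%) |
|---|---|---|
| 100% | 56.7 | 37% |
| 90% | 51.0 | 43% |
| 80% | 45.4 | 50% |
| 70% | 39.7 | 56% |

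**Step 2: rate ratio with identical behaviour.** With the follow-up offset it is (c1 × q)/(c0 × q) = c1/c0. With an answered-days offset it is q/q = 1.00.
- 80% against 100%: 0.80
- 90% against 80%: 1.125
- 90% against 70%: 0.90/0.70 = 1.29
- equal completion: 1.00

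**Step 3: comparison with the target effect.** Odds at 0.37 are 0.37/0.63 = 0.587. Multiplied by 1.28 they are 0.752, which is adherence 0.429 and non-adherence 0.571. The target is therefore a non-adherence rate ratio of 0.571/0.63 = 0.906. Completion of 0.906 × 90% = 81.5% in the CDST arm against 90% in the control arm would reproduce it with no change in behaviour.

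**Step 4: false-positive rate.** Simulated with no true difference, 90 days, 30 per arm, completion varying between people, and a Poisson model with robust standard errors. Ranges cover repeat runs.

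| Completion | Correlation 0.6 (plan's upper bound) | Correlation about 0.14 |
|---|---|---|
| 90% vs 80% | 12–13% | 28–30% |
| 90% vs 70% | 35–37% | 83% |

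The bias in the rate ratio is the same at both correlations; only the precision changes. With the log of answered days as offset, the rate ratio is 0.99 to 1.01 and robust false-positive rates are about 4% to 7%.

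**Step 5: standard errors.** At an assumed correlation of 0.1, model-based Poisson errors still gave 26% to 32% false positives with the answered-days offset, against 4.7% to 5.8% with robust errors. The offset alone is not enough.

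**The case against.** The strongest reply is that this is an undefined term, not a stated error. If length of follow-up means days answered, there is no bias. If unanswered days were counted as non-adherent, the bias would reverse: 80% against 100% completion would give (0.8 × 0.63 + 0.2)/0.63 = 0.704/0.63 = 1.12. This stands as a limit on the claim. But the ordinary reading is time under observation, and a denominator that can move the result either way needs a definition.

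The logistic model is also listed first, is the analysis to which the stated odds ratios correspond, uses answered days only, and does not have this fault; Phase 3 is a pilot. That stands, and it lowers the severity.

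Four stronger readings are tempting, and the documents do not support them.
- *Every missed entry counts as adherence.* Only the entry carrying the item matters. A missed afternoon entry affects none of stress, eating, sleep or preventive medication.
- *The CDST arm will complete more entries because it alone gets notifications.* Section 6.1.4 (Intervention Administration) points that way. But section 6.3.2 tells participants that both kinds of education appear as diary notifications, and section 6.1 describes the CDST reminders as responses to adherence behaviour, not prompts to complete the diary. Both arms also get completion feedback, contact after missed days and payment per entry. A gap between arms is possible but not shown.
- *The rate ratio could fall to 0.40 within the 80% rule.* Perfect mornings and afternoons would allow 0.8 × 3 − 2 = 40% of evenings. But the Phase 2 rule covers the first 30 days, and the rule covering all of Phase 2 governs entry to Phase 3. Neither bounds completion in a 90-day analysis set, and the case needs one group at 100% and the other at exactly 40% of evenings.
- *False-positive rates of 28% and 83% are what to expect.* They assume a correlation near 0.14, whereas the plan allows 0.6.

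**Conclusion.** The concern holds on the ordinary reading of length of follow-up, with unanswered days left out of the count. Non-adherence rates are understated in proportion to item completion. The rate ratio is multiplied by the ratio of completion between groups: 0.80 for 80% against 100%, and about 1.12 for 90% against 80%. With 30 per arm and robust errors, false positives are about 12–30% for 90% against 80% and about 35–83% for 90% against 70%, rising as within-person correlation falls from 0.6 to about 0.14.

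These figures rest on assumed completion gaps. The documents neither report nor predict one, and without a gap the rate ratio is unbiased. The fault is confined to the Poisson analyses in sections 6.4.3.1 and 6.4.3.2. It should be fixed, but it does not undermine the logistic analyses.

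**What to change.** In sections 6.4.3.1 and 6.4.3.2:
- Set the offset to the log of the number of days on which that strategy's item was answered: evening entries for stress, eating and preventive medication, morning entries for sleep.
- State that an unanswered day is counted as neither adherent nor non-adherent.
- For Treat Early, which is defined at the time a dose is taken, use the number of treated headache days or of recorded doses as denominator.
- Do not apply a daily offset to Avoid Overuse, which is a monthly measure.
- Use robust or over-dispersion-adjusted standard errors.
- Report item completion by arm and by predictor group beside each result.

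Section 6.4.5 should carry the same rule for the count outcomes. The cost is a short text change and one derived denominator per strategy, built from data already collected. It is best made before any analysis by arm.
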